3.7.3 Qualitative data analysis

Data Sources

The qualitative data from this study will include the following data sources:

- a) Handwritten notes and summaries of IDIs and KIIs
- b) IDI and KII debriefing reports
- c) Transcripts from audio-recorded KIIs, IDIs and FGDs.
- d) Summaries from the psychological assessments

Analysis Overview

The primary source of qualitative data used in the analysis will consist of raw textual data. Qualitative data will be audio-recorded, transcribed, translated into English and coded for qualitative analyses, using NVivo or a similar qualitative software. Data coding will be used as a primary analytical approach, for data reduction, that is, to summarize, extract meaning, and condense the data. The transcripts will be coded first through descriptive coding for key themes and topics, using a preliminary codebook. Additional codes will be identified through an iterative process of reading the textual data to identify emergent themes, and the codebook will be modified accordingly. In addition to descriptive codes, pattern codes, which achieve a greater level of abstraction, will be used to start linking themes and topics together. The analysis will be done by the investigative team, working interactively through regular face-to-face meetings, emails, and regular phone calls. The findings and interpretations of the data will be critically discussed until there is group consensus on the dominant themes and meanings contained in the data.

The primary final output of the qualitative analysis will include a synthesized report with representational quotes that will describe the health care provider and adolescent mothers' Knowledge Attitude and Practice (KAP) regarding adolescent reproductive health and pregnancy related services with pregnant and postnatal adolescent mothers and postdelivery care.

3.8 Data quality and management

SOPs will be developed for all data management process and procedures to ensure consistency and quality of data.

Quantitative data will be collected and entered by research staff on CRFs and Android electronic tablets (hand-held computers) using a computer-assisted personal interviewing (CAPI) software for the ACASI.

Qualitative data will be collected manually and on a voice recorder and will be transcribed into laptop computers by research assistants for subsequent coding in NVivo software and analysis. All discussions will be conducted in the local languages, will last no more than 90 minutes, and will be digitally recorded and transcribed into English. Interviewers/research assistants will have experience in qualitative methods including in-depth interviewing and probing where appropriate and relevant. Digital recordings will be transferred to secure computers and deleted from source computers.

All data clerks and managers will have received training on the requirements of strict confidentiality regarding patient identifying information, and laptop security. To protect detailed health and personal information data, study record keeping and access to participant identifying information will follow strict written SOPs and data will be subjected to a variety of quality control procedures. All records will be kept on password protected computers at MU-JHU. Participants will be identified primarily by their study number. All CRFs and identifiers will be kept in individual files in secured, access-limited room at the site. No individual participant identifier will be used in any reports or publications resulting from the study. Study investigators and coordinators will continuously mentor and monitor staff to ensure these procedures are followed according to SOPs in order to ensure data quality and confidentiality.

4 ANTICIPATED CHALLENGES AND MITIGATION PLANS

4.1 Maintaining Long –Term cohesion among peers

This will depend on the individual stability of the members, the group leader capability, and the quality of their relationships. This will require close monitoring and support by the group leaders and peer educators. We will ensure that there is continuous training, counseling and ongoing support sessions to address issues as they arise and support long-term cohesion including an understanding and commitment of protecting each other's privacy and not sharing confidential disclosures outside the group.

4.2 Stigma and discrimination:

HIV-related stigma and discrimination continue to be important issues in Uganda. MUJHU may be perceived as being associated with HIV research; so participants attending MUJHU may be suspected by others of being HIV-infected (despite many HIV-uninfected persons attending MUJHU). MUJHU will consult with youth and attempt to mitigate against this risk by rebranding and marking the lower building ground floor which has a separate entrance and exit as a

Youth-Friendly Service. Clinic services for teens will be on the ground floor and separated from other clinic and study populations.

4.3 Vulnerability of pregnant and postpartum women to relocate:

The time immediately after delivery may be associated with geographic displacement as many new mothers move for several weeks or months to their village of origin after delivery both because of the care needed by the new infant (and mother) and Uganda cultural norms among several tribes. We will attempt to minimize this through exploring this theme in our FGDs as well as our screening and enrollment procedures inquiring about intentions to remain within 30Kms of the clinic and encouraging women to advise of any temporary or permanent change in residence and maintain contact with the study team. We will also maintain regular contact with participants through their scheduled visits and by phone calls/sms using agreed general language with no mention of HIV or MUJHU).

4.4 Male partner and family involvement:

Male partner involvement continues to be a challenge in many parts of the country due to cultural, historical and structural factors. Among pregnant and postpartum adolescents there is a higher proportion without the ongoing support of male partners and a higher proportion dependent on their parents compared to adult women. In this intervention we will continuously encourage the participant to bring their partner/s to the education sessions on case by case basis and we will also encourage partner C&T.

4.5 Depression and psychological distress:

Pregnant adolescents and young mothers may be at a greater risk for anxiety and depression (including postpartum depression) and have a relatively low rate of health seeking behavior for their own health and that of their infants. While it is unlikely that the study itself would be causal (and would be more likely to assist young persons) the study evaluations are likely to identify any significant psychological distress or psychiatric disorder which would allow for early and appropriate referrals to an appropriate health provider (such as the Mulago Specialist Adolescent Clinic).

5 HUMAN SUBJECTS PROTECTIONS

5.1 Institutional Review Boards/Ethics Committees

This protocol and the associated consent documents and study-related documents (such as participation education and recruitment materials) will be reviewed by the primary IRB in Uganda and other regulatory bodies responsible for oversight of NIH sponsored research conducted in Uganda as well as regulatory bodies required by the sponsor. Any amendments to the protocol will be approved by the IRBs prior to implementation. Subsequent to the initial review and approval, the responsible IRBs will review the study at least annually in accordance with national requirements. Investigators will make safety and progress reports to the IRBs at least annually and within three months after study termination or completion. These reports will include the total number of participants enrolled in the study, the number of participants who completed the study, all changes in the research activity, and all unanticipated problems involving risks to human subjects or others.

5.2 Risk Benefit Statement

5.2.1 Risks

This study involves the vulnerable population of pregnant adolescents. Pregnant adolescents under the age of 18 are by definition considered emancipated minors.

The provision of routine clinical antenatal, delivery and postnatal services are not part of this study. Additional study related procedures do include provision of specific clinical services such as HIV and STI tests (requiring blood draws, vaginal swabs and urine specimens) as well as clinical examination and counseling and provision of contraception.

The main risks would be potential loss of privacy. The investigators will make all possible efforts to minimize risks to these adolescent study participants and to ensure confidentiality of the study participants and their study data. All staff will be trained on Human Subjects Protection and Good Clinical Practice. Before beginning the study, the investigators will have obtained approval from all relevant IRBs and from the Uganda National Council for Science and Technology (UNCST). The investigators will permit monitoring by relevant regulatory authorities, the NIH, applicable US/local government bodies, IRBs and UNCST, or their appointed agents. Subsequent to the initial review and approval, the responsible IRBs will review the study at least annually. Investigators will make safety and progress reports to the IRBs at least annually and within three months after study termination or completion. Adverse events will be reported according to local regulatory and NIH guidelines.

Since participation in the proposed clinical research includes the risks of loss of confidentiality and discomfort with the personal nature of certain questions asked as part of the study, every effort will be made to protect participant privacy and confidentiality. All participant information will be stored in locked file cabinets in secure areas with access limited to authorized study staff. Individual participants' study information will not be released without their written permission, except as necessary for regulatory monitoring, and/or auditing.

5.2.2 Benefits

Participants may benefit directly from the individual or group educational and supportive counseling provided, treatment for HIV and other STIs for themselves and/or their husband/partner/s and from counseling and provision and uptake of dual protection methods with effective contraception and barrier protection. Participants and others may benefit in the future from information learned from this study. Specifically, information learned in this study may help improve interventions which provide psychosocial support and education and prevent STIs/HIV and unwanted pregnancies among adolescent girls.

5.3 Informed Consent Process

Written informed consent will be obtained from all potential study participants including those emancipated minors aged 15 to 17 years following the National Guidelines for Research involving Humans as Research Participants issued by UNCST [31]. Parents or guardians need not be involved in the informed consent process since these adolescents are emancipated minors. However should the adolescents less than 18 years of age wish to include one or both parents (or their spouse/partner) in the informed consent process they will be free to do so.

Study staff will administer a comprehension checklist to potential participants prior to obtaining written informed consent to ensure that participants fully comprehend the nature of the study. In obtaining and documenting informed consent, the investigators and their designees will comply with applicable local and domestic regulatory requirements and will adhere to Good

Clinical Practices (GCP) and to the ethical principles that have their origin in the Declaration of Helsinki. Participants are always offered a copy of their informed consent form. The consent forms will clearly indicate the purpose of the study, the procedures to be followed, and the potential risks and benefits of participation, in accordance with all applicable regulations.

5.4 Participant Confidentiality

All study procedures will be conducted in private, and every effort will be made to protect participant privacy and confidentiality of client information. The study staff will implement confidentiality protections and the input of study staff and community representatives to identify potential privacy and confidentiality issues and strategies to address them. All study-related information will be stored securely at the study site. All participant information will be stored in locked file cabinets in areas with access limited to study staff. Participants' study information will not be released without their written permission, except as necessary for review, monitoring, and/or auditing IRB, regulatory bodies or sponsor.

5.5 Special Populations

This section outlines considerations made for the inclusion or exclusion of special populations in this study.

As pregnant adolescents have a high burden of disease and social exclusion/stigma and this study is purposely designed to assess acceptability and effectiveness of strategies to address these issues it is critical that pregnant adolescents is included as the study population. The risks associated with participating in the study are minimized and mitigated by the study design. As such they meet the ethical criteria of being both at risk and standing to benefit from the proposed interventions.

We have determined however that pregnant adolescents with significant comorbidity or fetal loss should be excluded from the study as they would be likely not to be able to comply with the study requirements (of visit attendance) and/or would require additional specialized counseling and other support over that available within the study.

5.5.1 Pregnant Women

Pregnant women will be offered enrollment in this study in accordance with guidelines set forth in the Ugandan ethics guidelines [31] and current US guidelines.[39] Given that the primary purpose of the research is to meet the health needs of the mother informed consent will not be sought from the father of the baby. However should the pregnant women wish to include her spouse in the informed consent process they will be free to do so.

5.5.2 Children

This study plans to include emancipated minors as study participants; that is pregnant children who are aged 15 to 17 years at the time of enrollment.[31] Informed consent procedures follow Uganda ethical requirements for emancipated minors.

5.6 Compensation

Compensation for participants' time and travel will be provided to participants at a rate of 10,000 Uganda shillings per scheduled study visit.

Of note if FGD and IDIs are scheduled on a separate day to other study visits these would be considered as a scheduled study visit. If scheduled on the same day as a scheduled study visit an additional 5,000 Uganda shillings would be paid to compensate participants for the additional time involved.

If a study participant moved more than 30kms away (despite indicating they would stay within 30kms in the enrollment interview) or experienced transport costs greater than 10,000 Ugandan shillings, the study team would reserve the right to consider this on a case by case basis with the possibility of reimbursing actual transport costs.

5.7 Access to HIV-related Care (HIV Counseling and Testing and HIV care)

HIV testing for participants will be offered together with pre-test and post-test counseling by trained study counselors. Referral for additional counseling will occur if identified as a need by the counselor or the participant. Participants diagnosed as HIV-positive will receive appropriate referrals to nearby adolescent HIV care and treatment services at the Baylor Adolescent Clinic (Centre of Excellence) for ongoing management. Sexual partner/s of teen participants with positive HIV or other STI tests will be invited to attend the clinic and receive counseling, testing, treatment (if applicable) for other STIs and referred for appropriate services. HIV exposed infants will also be followed up appropriately in the PMTCT program the mother is referred to.

5.8 Study Discontinuation

This study may be discontinued at any time by NIAID, the OHRP, other governmental or regulatory authorities, or site IRBs/ECs

6 PUBLICATIONS AND DISSEMINATION OF STUDY FINDINGS

6.1 Dissemination of findings:

Research findings will be shared with all the stakeholders including study participants, CAB members, participating health facilities' staff, Ministry of Health, the Ugandan Society for Adolescent Health, PEPFAR and donor representatives and other policymakers. The implementation science findings will also be submitted for presentation at regional and international meetings and for publication/s in the peer-reviewed scientific literature.

6.2 Sustainability:

Both the Ministry of Health Reproductive Health staff and the Makerere University Department of Obstetrics/Gynecology are highly supportive of this project as noted in their letters of support. If either or both of the enhanced adolescent group or individualized peer support interventions show acceptability, feasibility coupled with significantly improved uptake of effective contraceptives and barrier protection and reduced incidence of HIV/STIs when compared to the routine care control group, the investigators will work with MOH, PEPFAR and other donors to mobilize resources and implement these adolescent reproductive services in other parts of Kampala and other health districts across Uganda.

APPENDIX A: ADDITIONAL BACKGROUND ON THE CONCEPT AND USE OF THE HEALTH BELIEF MODEL

Table from "Theory at a Glance: A Guide for Health Promotion Practice" (1997)

Concept	Definition	Application
Perceived Susceptibility	One's opinion of chances of getting a condition	Define population(s) at risk, risk levels; personalize risk based on a person's features or behavior; heighten perceived susceptibility if too low.

Perceived Severity	One's opinion of how serious a condition and its consequences are	Specify consequences of the risk and the condition
Perceived Benefits	One's belief in the efficacy of the advised action to reduce risk or seriousness of impact	Define action to take; how, where, when; clarify the positive effects to be expected.
Perceived Barriers	One's opinion of the tangible and psychological costs of the advised action	Identify and reduce barriers through reassurance, incentives, assistance.
Cues to Action	Strategies to activate "readiness"	Provide how-to information, promote awareness, reminders.
Self-Efficacy	Confidence in one's ability to take action	Provide training, guidance in performing action.

Conceptual Model

Source: Glanz et al, 2002, p. 52

Scope and Application

The Health Belief Model has been applied to a broad range of health behaviors and subject populations. Three broad areas can be identified (Conner & Norman, 1996):[40]

1) Preventive health behaviors, which include health-promoting (e.g. diet, exercise) and health-risk (e.g. smoking) behaviors as well as vaccination and contraceptive practices. 2)

Sick role behaviors, which refer to compliance with recommended medical regimens, usually following professional diagnosis of illness.

3) Clinic use, which includes physician visits for a variety of reasons.

APPENDIX B: SCHEDULE OF STUDY VISITS AND EVALUATIONS

	SCR/ ENR	36 weeks APT	Birth †	6 weeks PPT	10 weeks PPT	3 months PPT	6 months PPT	9 months PPT
ADMINISTRATIVE AND REGULATORY								

Obtain Informed Consent	X							
Assign a unique Participant Identification (PTID) number	X							
Asses and/or confirm eligibility	X							
Collect/review /update locator information	X	X	X	X	X	X	X	X
Randomization	X							
Provide reimbursement	X			X	X	X	X	X
Schedule next visit	X	X		X	X	X	X	X
INTERVENTION								
Enhanced Counseling Education Sessions/Routine care as provided	X			X	X	X	X	X
BEHAVIORAL								
Behavioral Assessments using IAQ and ACASI	X				X		X	X
Psychosocial Assessment	X							X
HIV pre and post test counseling	X					X		X
Provision of Condoms	X	X	X	X	X	X	X	X
Conduct Social harms assessment					X		X	X
CLINICAL								
Obtain/review and update RH and Medical History	X	X	*	*	*	*	*	X
Clinical Examination – Blood Pressure, Weight, Obstetric exam	X	X						
Prescribe contraceptives				X	*	*	*	*
Provide available test results	X	X		*	*	X	*	X
Provide treatment/referral as appropriate	*	*		*	*	*	*	*
LABORATORY								
Blood	HIV-1 Serology (rapid tests)	X					X	X
	Syphilis serology	X					€	X
	RPR (TPAB if positive)							
Urine	Protein and Glucose	X	X					
	Rapid test for Gonorrhea infection	X	*		*	*	*	X
	Rapid test for Chlamydia infection	X	*		*	*	*	X
	HCG test				*	*	*	X
Pelvic	Rapid test for Trichomoniasis (self collected vaginal swab)	X	*		*	*	*	X
	Collect Vaginal swab for Bacterial Vaginosis testing	x	*		*	*	*	X

Collect vaginal swab for testing presence of Y chromosome ‡								X
QUALITATIVE COMPONENT								
Serial In-depth Interview (SIDI)	X				X			X
Focus Group Discussion (FGD)	X							X
Single In-depth Interview (IDI)				*	*	*	*	*

X mandatory, *If indicated †only for intervention groups, € repeat at 6months if positive at enrolment, ‡done only at study exit for participants with self reported condom use.

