We will conduct a 3-arm, randomized, controlled trial of 519 pregnant adolescents aged 15 through 19 years at enrollment to test the acceptability and effectiveness of two enhanced adolescent friendly reproductive health prevention interventions versus current routine care. In each intervention group, 152 adolescent mothers will be randomized to either the enhanced group peer support education and counseling intervention or to the enhanced one-to-one (individual) peer support education and counseling group with a young, model, peer educator trained to deliver RH education and counseling messages, beginning during pregnancy (≥ 28 weeks) and followed up to 9 months postpartum or study end at or after 6 months (whichever comes first). The control group will consist of 215 adolescent mothers randomized to routine care as provided at Mulago hospital (or the designated health facility) where midwives deliver group sessions during antenatal and postpartum care visits as well as standard PMTCT services including routine opt-out HIV C&T and availability of partner C&T. Syphilis testing should also be routinely provided and treatment provided for infected pregnant mothers and their partners as per local standard of care.

The 3 groups will be enrolled with study visits at 3, 6 and 9 months post-partum however the intervention groups (Arms 2 and 3) will have additional visits at 36 weeks Antepartum, delivery, 6 and 10 weeks postpartum, Quantitative baseline data will be collected on routine demographic characteristics, reproductive history, pregnancy intentions and sexual risk/perceptions and HIV/STI status.

Summarized table 1 of the study schedule and evaluation

	SCR/ ENR	36 weeks APT	Birth†	6 weeks PPT	10 weeks PPT	3 months PPT	6 months PPT	9 months PPT†
Arm 1– Routine Care	X					X		X
Intervention: Enhanced Counseling Education Sessions/Routine care as provided	X			X	X	X	X	X
Behavioral Assessments using IAQ and ACASI	X				X		X	X
Psychosocial Assessment	X					X		X
Obtain/review and update RH and Medical History	X	X	*	*	*	*	*	X
Clinical Examination – Blood Pressure, Weight, Obstetric exam	X	X						
Prescribe contraceptives				X	*	*	*	*
Provide available test results	X	X		*	*	X	*	X
Provide treatment/referral as appropriate	*	*	*	*	*	*	*	*
LABORATORY								
Blood	HIV-1 Serology (rapid tests)	X					X	X
	Syphilis serology RPR (TPAB if positive)	X				€		X
Urine	Protein and Glucose	X	X					
	Rapid test for Gonorrhoea infection	X	*		*	*	*	X

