3.3.3 In-depth Interviews (IDI)

Serial IDIs (SIDI) with 12 randomly preselected pregnant adolescents (4 each arm) will be conducted at baseline, 10 weeks and at study exit. Participant's attitudes, beliefs and practices towards pregnancy and RH services will be collected using behavioral CRFs at baseline, 10 weeks and study exit to assess any changes over time. In addition, participants HIV/STI risk perception and motivation to utilize RH services including condom use will also be assessed.

Single In-depth Interviews will also be conducted for participants who seroconvert, become pregnant, or those who acquire 2 or more episodes of STIs during the study duration. Serial In-depth Interviews will be conducted for randomly pre-selected participants at baseline, 10 weeks and about 2 weeks post study exit. In the event that a participant selected for a serial IDI either seroconverts, becomes pregnant, or acquires 2 or more episodes of STIs, then the last IDI will be conducted at the point when the end point occurs.

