	Urine	 Collect Urine (20mls) 
  Rapid test for Gonorrhea infection  Rapid test for Chlamydia infection
	Pelvic	
 • Collect vaginal swab for rapid Trichomonas vaginalis testing • Collect swab for Bacterial vaginosis testing (PH, Whiff and Clue cells)

Enhanced Peer Support Education and Counseling (Intervention)	Depending on the group the participant is randomized to, the intervention will be done around 4 weeks after enrolment as this is logistically appropriate for the study. Participants in Arm 2 will be put in homogenous groups (similar gestation, age group and language preference) of 8 – 12 adolescents, while the Arm 3 participants will schedule their individual follow-up visits on the same day as their clinic visits. Participants in the Control Arm will receive routine antenatal, delivery and follow-up services with next study visit at 3 months postpartum
Qualitative component	Participants preselected for the serial IDIs and FGDs will have the baseline interviews and FGDs within 3 weeks of enrolment prior to receiving the intervention

The participant will be provided with an appointment card (usual cards used in the ANC/PNC clinics) however a round colored sticker (different colors for each study arm) will be placed on the card to differentiate the 3 study groups.

STI treatment will be provided for any curable STI diagnosed at screening and in follow-up for the participant and her partner/s in accordance with national treatment algorithms.[33-34] Participants found to be HIV positive (by two separate rapid tests) will not be excluded from this proposed study but will be counseled, encouraged to disclose to their partner/s and will receive PMTCT services including Option B+ with ARV treatment for life as per national guidelines. As part of PMTCT services they will be encouraged to invite their partner/s for HIV C&T and their HIV-exposed infants will be followed up with linkages to ongoing services. Participants with positive syphilis tests will be treated and have repeat testing done per local national guidelines and also at the final visit.

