3.5.1 Follow-up and Study Exit Visits

3.5.1.1 Every month after enrolment during pregnancy through delivery and at 6, 10 and 14 weeks and 6 and 9 months postpartum

During follow-up the study procedures and STI screening tests will be done as summarized in the table below.

Table 3: Week 36 Antepartum, Delivery, Week 6 and 10, Month 3, 6 and 9 Postpartum

Component	Procedure/Analysis
Administrative and Regulatory (all visits including delivery contact for intervention groups)	
 Review/update locator information Provide reimbursement for study visit* Schedule next visit
Behavioral (at 3, 6 and 9 months)	
 Conduct behavioral assessment HIV pre- and post-test counseling†
Clinical (at 36 weeks Antepartum, and as indicated)	
 Review and update RH and Medical History Perform Clinical Examination‡ Prescribe/provide preferred contraceptive method Provide available test results Provide treatment/referral as appropriate

Laboratory	Blood	 Collect Blood  2mls for HIV-1 Serology (rapid tests)†  2mls for Syphilis serology RPR (TPAB if positive)
	Urine	 Collect Urine (20mls)  Rapid test for Gonorrhoea infection  Rapid test for Chlamydia infection  Urine for Protein and glucose¥
	Pelvic	
 • Collect vaginal swab for rapid Trichomonas vaginalis testing • Collect swab for Bacterial vaginosis testing (PH, Whiff and Clue cells) • Collect vaginal swab for testing presence of Y chromosome ‡
Enhanced Peer Support Education and Counseling (Intervention) (at 6, 10 and 14 weeks ,6 and 9 months)		
Depending on the group the participant is randomized to, the intervention will be done ± 2 weeks at all scheduled study visits. This is to allow flexibility in scheduling the sessions for the intervention groups
 
Participants in the Control Arm will have the routine care provided to postpartum in the postnatal clinic

Qualitative component		
Participants preselected for the serial IDIs and FGDs will have the final interviews and FGDs within 2 weeks of the scheduled final education and support session at study exit.
 
In addition, single IDIs will be conducted for participants who

		
seroconvert, have ≥ 2 STIs or have recurrent pregnancy at any time during follow-up.

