3.5.2 Behavioral Evaluations

Behavioral evaluations assessed by ACASI and interviewer administered questionnaires include;

- Frequency of unprotected sex (self-report of penetrative sexual intercourse since previous visit)/report of condom use
- Risk behaviors – including any new sexual partners/ encounters, concurrent sexual partners (stable or casual), alcohol/drug use, domestic violence e.t.c.
- HIV/STI risk perception and motivation to utilize RH and pregnancy related services
- Reproductive intentions and family planning
- Male partner/s involvement – presence, cohabitation, economic, psychosocial support, health care support, gender based violence etc

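### The first postpartum social-harms assessment is at 10 weeks in the peer arms but at 6 or 9 months in control, because Appendix B uses a visit that control lacks and leaves the shared 3-month visit blank

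*Combined protocol and SAP*

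**What the plan says.** **Visits.** Section 3.1 states: "The 3 groups will be enrolled with study visits at 3, 6 and 9 months post-partum". It then adds that "the intervention groups (Arms 2 and 3) will have additional visits at 36 weeks Antepartum, delivery, 6 and 10 weeks postpartum". Table 2 in Section 3.5 agrees for control: "Participants in the Control Arm will receive routine antenatal, delivery and follow-up services with next study visit at 3 months postpartum". The Arm 1 row of Table 1 is marked at enrolment, 3 months and 9 months. It has no mark at 10 weeks and, unlike the Section 3.1 text, none at 6 months.

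**Social harms.** The row "Conduct Social harms assessment" appears only in Appendix B, with marks at 10 weeks, 6 months and 9 months. The form is not defined, no recall period is given, and it is not listed among the endpoints in Section 3.6.

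**Violence items.** Section 3.5.2 puts them in the behavioural evaluations, which cover "concurrent sexual partners (stable or casual), alcohol/drug use, domestic violence" and, under male partner involvement, gender-based violence. That questionnaire has two follow-up schedules. The row "Behavioral Assessments using IAQ and ACASI" in Table 1 and Appendix B is marked at enrolment, 10 weeks, 6 months and 9 months. Table 3 in Section 3.5.1 instead says "Behavioral (at 3, 6 and 9 months". Nothing states which one governs.

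**The concern.** A by-arm description of harms can be read only where every arm was asked at the same times. Here the early postpartum question is tied to a visit that belongs to the interventions, and the nearest visit shared by all arms is skipped. More frequent and earlier asking can by itself produce more reports in the peer arms. Longer recall in control can hide events there.

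The subject is not remote for this population. Section 1.1 gives 58% as the share of girls this age who report physical or sexual violence. Section 1.3 describes peer training with role play on negotiating condom use. Whether that raises or lowers partner violence is unknown, and this is the reason to ask all arms alike. Section 4.3 also expects many mothers to move away for weeks or months after birth, so a late first question misses some of them.

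**Working it through.** No sample-size or power figure is involved. The check sets the schedules side by side and counts.

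**1. Are the columns read correctly?** Two other Appendix B rows can be checked against text. HIV counselling reads enrolment, 3 and 9 months, and the notes under Table 3 give 3 months and study exit. The serial interview reads enrolment, 10 weeks and 9 months, and Section 3.3.3 gives baseline, 10 weeks and exit. The alignment holds.

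**2. Schedules**

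| Item and source | Enrolment | 10 weeks | 3 months | 6 months | 9 months |
|---|---|---|---|---|---|
| Social harms, Appendix B | – | X | – | X | X |
| Behavioural, Table 1 and Appendix B | X | X | – | X | X |
| Behavioural, Table 3 (follow-up only) | n/a | – | X | X | X |
| Peer-arm visits, Section 3.1 | X | X | X | X | X |
| Control visits, Section 3.1 text | X | – | X | X | X |
| Control visits, Table 1 Arm 1 row | X | – | X | – | X |

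**3. Social-harms assessments per woman**
- Peer arms (152 + 152 = 304 women): 10 weeks, 6 and 9 months = 3, or 304 × 3 = 912 scheduled.
- Control (215 women), Section 3.1 text: 6 and 9 months = 2, or 215 × 2 = 430.
- Control, Table 1 Arm 1 row: 9 months = 1, or 215 × 1 = 215.
- Women whose exit visit is month 6: peer 2 (10 weeks, 6 months), control 1 (6 months).

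**4. Before the 3-month visit.** Scheduled for a social-harms assessment: 304 of 304 peer-arm women and 0 of 215 control women. Four control women have a 10-week serial interview, for which data "will be collected using behavioral CRFs at baseline, 10 weeks and study exit". That is a qualitative contact and not a study visit for the arm.

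**5. Lag in the first assessment.** Taking 6 months as 26 weeks and 9 months as 39 weeks, control is later by 26 − 10 = 16 weeks (Section 3.1 text) or 39 − 10 = 29 weeks (Table 1).

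**6. Behavioural questionnaire, postpartum.** On Table 1 and Appendix B the counts are again 3 against 2 or 1. On Table 3 they are 3 against 3 with the Section 3.1 text, or 3 against 2 if Arm 1 has no 6-month visit.

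**7. Women lost.** At the 10% loss in Section 3.7.1, 215 × 0.10 = 21.5, about 22 control women over the whole follow-up. At the 95% retention target in Section 3.5.6, 215 × 0.05 = 10.75, about 11. Neither section says when losses occur. On the Section 3.1 text, those lost before 6 months leave with no postpartum social-harms assessment. On Table 1 all of them do. So 11 to 22 is an upper range.

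**8. After adding 3 months for all arms.** At shared visits the counts are 3 v 3 (Section 3.1 text) or 2 v 2 (Table 1: 3 and 9 months). Month-6 exits have 2 v 2.

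**The case against.** A reader might infer that control has no early harms data, or that harms in control would go unseen. The documents do not support that. The behavioural questionnaire is given to every arm at enrolment. Section 3.5.3 and Table 1 schedule psychosocial risk assessment by HEADDSS at 3 months, a visit all arms attend, although Appendix B omits that mark. No recall window is stated for the social-harms form, so a 6- or 9-month question may reach back over the early months. Elsewhere the protocol does use look-back periods. Sections 5.1 and 5.2.1 keep safety and adverse-event reporting in place. All this stands. It reduces the problem to later and less frequent ascertainment. HEADDSS is not the social-harms form, however, and no later question reaches a woman already lost.

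A second argument is that the documents do not treat every additional visit as strictly peer-only. Appendix B puts its intervention-only dagger on birth alone, and a note under Table 3 has urine tested at 36 weeks in all groups. That is fair for 36 weeks. For 10 weeks, Section 3.1, Table 2 and the Arm 1 row of Table 1 all agree that control has no study visit.

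Third, social harms is not an endpoint and Section 3.7.2 plans no comparison of it. This also stands and limits the weight of the point.

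Finally, moving the 10-week assessment to 3 months would delay detection in the arms that receive the intervention, and some women who relocate will miss 3 months too. The first part is right, so 3 months should be added and 10 weeks kept. The second means that the change helps but does not close the gap completely.

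**Conclusion.** The point holds as a schedule fault with a cheap remedy. As written, the peer arms have their first postpartum social-harms assessment 16 or 29 weeks before control, and 3 scheduled assessments per woman against 2 or 1. The range depends on whether Arm 1 has a 6-month visit, which the documents leave open. The violence items share the imbalance if Table 1 and Appendix B govern. If Table 3 governs together with the Section 3.1 text, they do not.

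The consequence is longer recall and fewer questions in control, and no postpartum social-harms assessment for control women lost before their first one. How many that is cannot be said, because the timing of loss is not given. The conclusion assumes the schedules are followed as printed. No primary outcome, sample size, power or error rate is affected.

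**What to change.** 1. In Appendix B, add the social-harms assessment at 3 months for all arms.
2. In Table 1 and Appendix B, add the behavioural assessment at 3 months for all arms, in line with Table 3, and state that this schedule governs.
3. Keep the 10-week social-harms question in the peer arms for participant safety, and list those reports separately by arm. Word the 3-month form to cover the same period in every arm. Otherwise the peer arms would report only on the weeks since their 10-week answer.
4. State whether Arm 1 has a 6-month visit.
5. In Section 3.7.2, add a sentence: any by-arm description of harms and violence uses visits common to all arms (3 months, 6 months if attended, study exit), shown as n/N with the number not assessed.

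The cost is a longer 3-month visit and a protocol amendment, which needs IRB approval under Section 5.1. No visit, laboratory test or participant is added, since every version of the schedule brings all arms in at 3 months. The change helps only if made before those visits take place.
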